6.0 REQUIRED EVALUATIONS, TESTS, AND OBSERVATIONS

6.1 Pre-Screening Evaluations for Eligibility

Pre-screening will occur to determine eligibility prior to scheduling participants for their campus visit. If the participant appears eligible based upon telephone screening, a SJLIFE study visit will be scheduled. The remaining evaluations for study eligibility will occur prior to randomization on the study. All of the evaluations have been described in detail in section 4 above.

Baseline Measures: Baseline evaluation for all participants will include a medical evaluation, neurocognitive assessment, and collection of biological samples. Because evaluations performed, as detailed in the Children's Oncology Group "Long-Term Follow-Up Guidelines for Survivors of Childhood, Adolescent, and Young Adult Cancers," are standard care in the SJLIFE clinic, no additional monetary funds will be required for the baseline medical or neurocognitive evaluation in the proposed study cohort. Medical evaluations are based on primary cancer diagnosis, age at diagnosis, and therapeutic interventions and are limited to screening and diagnostic evaluations to characterize cancer-related health complications. Complete treatment records, including all information from all medical follow-up, will be available to study investigators. [name] is the Director of the SJLIFE clinic and carefully reviews and approves each abstracted treatment summary and medical history. The existing data give us the ability to carefully evaluate whether patients in our study are similar to or differ from nonparticipants. Table D summarizes the pre-screening evaluations and baseline measures.

Table D: Pre-screen and Baseline Measures

Evaluations – must be obtained prior to randomization	Prescreen	Baseline Visit
Inclusion/Exclusion criteria questions	X ¹	
Sleep-related questions		X
Informed consent		X
HIPAA		X
Standardized Sleep Measures		X
Melatonin		X ³
Correlative Psychosocial Measures		X ²
PRISE (side effect monitoring)		X
Neurocognitive Assessment Measures		X ²
Pregnancy Test**		X ²
History and Physical Exam		X ²

** The St. Jude IRB requires that a female patient of childbearing potential must have a negative pregnancy test as a condition of clinical research eligibility.

¹Mailed with introductory letter.

²Completed as part of SJLIFE protocol

³Optional

6.2 Evaluations During Therapy

After completion of the campus visit, participants will complete a five (5) day home-based sleep assessment to include actigraphy and a daily sleep diary. Participants will be contacted after the first week ± 7 days of taking the study drug and biweekly ± 7 days thereafter to monitor for side effects and adverse events. Monthly ± 10 days, research participants will be asked to conduct a pill count and report the number of pills remaining in their medication vial as a measure of treatment adherence. Three (3) months ± 1 week into the intervention trial, participants will complete objective and subjective sleep measures at home, including five days of actigraphy, a daily sleep diary, and standardized sleep measures. These data will allow for the examination of short-term effects of melatonin on sleep parameters. Table E summarizes the evaluations to be completed during therapy.

Table E: Evaluations During Therapy

Evaluation	7-10 days after baseline visit	Monthly (± 10 days)	3 months (± 1 week)	6 months (± 4 weeks)
• Actigraphy	X ¹		X ¹	X ¹
• Daily Sleep Diary	X ¹		X ¹	X ¹
• Standardized Sleep Measures			X ¹	X ¹
• Side effect monitoring	X ²	X ²		
• Study drug adherence (Pill Count)		X ³		
• Correlative Psychosocial Measures				X ¹
• Interim History and Visit with a Medical Provider				X
• Neurocognitive Assessment Measures				X
• Melatonin				X ⁴

¹Completed at home.²Initially after the first week ± 7 days of taking study drug, then biweekly ± 7 days for the duration on study.³Obtained every 30 days ± 10 for duration on study.⁴Optional

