4.2 Sleep Measures

Sleep parameters will be assessed at three time points during the study: Baseline, 3-months, and 6-months. The Baseline assessment will occur prior to initiation of the melatonin intervention. The two follow-up assessments will occur while participants are actively enrolled on the intervention trial. Each assessment will include the objective and subjective measures as outlined below.

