4.2.1 Actigraphy

Sleep-pattern measures of each participant will be measured with Actigraphy to be worn over 5 consecutive days at three specified intervals [Baseline, 3 months, 6 months]. Actigraphy provides objective assessment of wrist movement that infers wakefulness and sleep. Functionally, the actigraph provides sleep-pattern measures including: sleep onset latency (SOL), wake after sleep onset (WASO), and total sleep time (TST). Movement triggering the actigraph is relatively high during wakefulness and decreases to near-zero values during sleep. The actigraphy will collect data in the zero crossing mode, where the transducer signal is compared with a fixed sensitivity threshold. The number of times the signal voltage

crosses the reference voltage is accumulated in temporary memory storage until the user-defined epoch length has transpired.

[Acceleration Index—the acceleration index (AI) is calculated by the formula: $AI=2p-1$]

Where p is the proportion of the interval required for 50% of the total activity in the interval to be completed. For example, for a 1-hour interval, if the activity total for the interval was 1000 and 800 counts occurred in the first 20 minutes of the interval, p would be 20/60 or .33. Doubling p and subtracting 1 scales the index from -1 to +1. Thus, negative values represent slowing during the interval, 0 represents uniform distribution of activity during the interval, and positive values represent acceleration during the interval.

Analysis of actigraphic records reveals sleep-wake patterns that correlate closely with patterns obtained via polysomnographic recordings and behavioral observations.⁶⁰⁻⁶⁷ Furthermore, actigraphy is a reliable method for assessing sleep-wake patterns and monitoring of treatment response among insomnia patients.⁶⁷ The American Academy of Sleep Medicine practice parameters state that actigraphy is an accurate estimate of sleep patterns in normal healthy adults and there is evidence to support the use of actigraphy to describe sleep patterns among those with insomnia and as a study outcome measure.⁶⁸ Actigraphy is able to sensitively capture change in sleep-wake patterns before and after behavioral or medical interventions, and actigraphic data from either wrist is highly similar.

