11.0 STATISTICAL CONSIDERATIONS

The primary focus of this study is to evaluate the efficacy of melatonin on neurocognitive functioning in long term survivors of childhood cancer. Currently, there are 2,331 survivors potentially eligible for this study and 1,410 (61% have been identified as expected to have least one area of neurocognitive impairment. Further, it is estimated that among all the eligible survivors roughly 30% will have delayed sleep (sleep onset latency ≥ 30 minutes). Thus, the eligible survivors can be classified into three distinct cohorts (I) Those who are neurocognitively impaired but don't have delayed sleep 987 (II) Those who are neurocognitively impaired and have delayed sleep 423, i.e. 30% of 1,410, and (III) Those who don't have neurocognitive impairment but have delayed sleep problems (this would be roughly 30% (276) of those who are not neurocognitively impaired. Targeted enrollment for the study is 987 survivors and expected evaluable is 395.

[figure not shown]

Figure 2. Three group stratification with parallel allocation to melatonin/placebo

Primary Objective: Examine the efficacy of melatonin treatment on neurocognitive functioning in adult survivors of childhood cancer.

- Hypothesis 1: Long-term survivors of childhood cancer with documented baseline neurocognitive deficits (Cohorts 1 and 2), in attention, memory,

and/or executive functioning, randomized to the melatonin treatment arm, will demonstrate improved neurocognitive performance following six months of treatment compared to those randomized to placebo.

The primary objective of this study is to demonstrate that treatment with melatonin will be associated with improvement in neurocognitive performance. This will be evaluated in Cohorts 1 and 2 independently. The study will be conducted by randomizing survivors to melatonin or placebo within each of the two Cohorts.

For those who are in Cohorts 1 and 2 baseline neurocognitive evaluation along with other evaluations will be obtained prior to randomization to melatonin or placebo arm. After randomization, sleep data will be collected using actigraphy in week one when the survivors are in their homes. The intervention will be delivered for a period of six months with regular phone calls for monitoring. Then one week before the six month visit sleep data using actigraphy will be collected. The neurocognitive data will be collected at the 6 month return visit (post-treatment).

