Appendix I: Schedule of Evaluations

Evaluation	Eligibility	Baseline	On-Study			End
	Pre-Screen	Study Entry	Within 7–10 days of baseline visit	Monthly (± 10 days)	3 months (± 1 week)	6 months (± 28 days)
Inclusion/Exclusion criteria questions	X ¹					
Sleep-related questions		X				
Informed consent		X				
HIPAA		X				
Standardized Sleep Measures		X			X ³	X ³
Neurocognitive Assessment Measures		X ²				X
Correlative Psychosocial Measures		X ²				X ³
Pregnancy test		X ²				
History and Medical Provider visit		X ²				X
Actigraphy			X ³		X ³	X ³
Daily Sleep Diary			X ³		X ³	X ³
Side effect monitoring		X	X ⁴			
Study drug adherence (Pill Count)				X		

¹Mailed with introductory letter

²Completed as part of SJLIFE protocol

³Actigraph and sleep measures mailed to participant's home for completion. Standardized sleep measures completed at home at 3 months and 6 months. Correlative psychosocial measures completed at home at 6 months.

⁴Initially completed after 7-10 days on study medication; then bi-weekly for remainder of study.

[figure not shown]

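### Section 4.2 requires baseline actigraphy and diary before treatment, but the schedule lists them as on-treatment evaluations and nothing fixes the first tablet relative to them

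*Combined protocol and SAP*

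**What the plan says.** Section 4.2 sets the rule for the three sleep assessments: "The Baseline assessment will occur prior to initiation of the melatonin intervention". It adds that each assessment contains both the objective and the subjective measures. Sections 4.2.1 and 4.2.2 make these five consecutive days of actigraphy and a matching five-day diary. Appendix II lists both at baseline, 90 days and 6 months, so there is one baseline recording per participant.

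The schedule places that recording as follows:

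- **Section 6.1, Table D** lists the evaluations that "must be obtained prior to randomization". It includes the standardized sleep questionnaires but neither actigraphy nor diary.
- **Section 6.2** covers evaluations during therapy and says: "After completion of the campus visit, participants will complete a five (5) day home-based sleep assessment to include actigraphy and a daily sleep diary". Its Table E puts actigraphy, diary and the first side-effect contact in the column "7-10 days after baseline visit". A footnote times the contact at one week of study drug, give or take seven days.
- **Appendix I** puts the same three items under its on-study heading, in the column "Within 7–10 days of baseline visit". Footnote 3 says the actigraph is mailed to the home. Footnote 4 times the first side-effect check after seven to ten days on the tablets.
- **Section 11**, describing Cohorts 1 and 2, says: "After randomization, sleep data will be collected using actigraphy in week one when the survivors are in their homes". The next sentence is: "The intervention will be delivered for a period of six months with regular phone calls for monitoring".

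Section 4.5 says that tablets are sent by courier with two-day delivery. No section gives the date of the first tablet or ties it to the end of the recording.

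**The concern.** The rule in Section 4.2 protects a pre-treatment value. Staff who work from Table E or Appendix I see the recording as an on-treatment item, next to a contact that presupposes drug exposure. A participant could start tablets on delivery and wear the actigraph afterwards without departing from either table.

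If that happens, any effect already present in the melatonin arm enters its baseline and is subtracted from its change score. The placebo arm has no matching loss, so the between-arm difference in change moves toward zero. With only one baseline recording planned, the lost value cannot be recovered.

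The exposure is limited to actigraphy and diary change scores. It matters for the first secondary objective, and for the Cohort 2 correlation between latency change and neurocognitive change, only if latency is taken from one of those two sources. The plan does not settle this. Section 7.1 speaks of subjective and objective sleep parameters, while the latency power text in Section 11 names only the PSQI.

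**Working it through.** **1. Which entries conflict with Section 4.2.** The rule concerns the start of the intervention, not randomisation. Table D's omission and Section 11's post-randomisation timing are therefore compatible with it, though neither adds a safeguard. The conflict lies in the placement of the recording in Table E and in Appendix I.

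**2. Whether the columns leave five tablet-free nights.** Let day 0 be the campus visit, d the night of the first tablet, c the day of the first side-effect check, and s the first recording night. Nights s to s+4 are tablet-free only if d ≥ s + 5.

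- *Appendix I, footnote 4 read together with its column heading:* c ≤ 10 and c − d ≥ 7, so d ≤ 10 − 7 = 3. At most 3 nights after the visit are tablet-free (4 on inclusive counting), against 5 needed. Mailing the actigraph home would reduce this further.
- *Appendix I, footnote 4 on its own medication clock:* the column puts no limit on d, and nothing follows about the recording.
- *Table E:* c is 7 to 10 with 0 to 14 days on drug, so d can be anything from 0 to 10. Five tablet-free nights fit if s + 5 ≤ 10, that is, if the recording starts by day 5. If it starts on day 7 to 10, as the column literally says, a tablet-free recording needs d ≥ 12 to 15, which is after that column's own side-effect check.

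The tables therefore permit an overlap but do not require one.

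**3. Illustration of size.** Inputs from Section 11: a 15-minute difference, SD 27.7, test-retest correlation 0.70, 66 and 65 participants in Cohort 2, α = 0.05. The plan states 80% power for these inputs. A two-sided two-sample t-test at 0.05 gives 87%; 80% appears at α = 0.025. That discrepancy is a separate matter. If the correlation is used, the change-score SD is 27.7 × √(2 × (1 − 0.70)) = 21.5.

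Assumptions not in the documents: k of the 5 nights are on tablets, a share g of the effect (0 to 1) is present on such a night, and latency is averaged over the five nights. The expected difference in change is then 15 × (1 − g × k/5).

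| k | g | Difference (min) | Power, SD 27.7 | Power, SD 21.5 |
|---|---|---|---|---|
| any | 0 | 15 | 87% | 98% |
| 1 | 1 | 12 | 69% | 89% |
| 2 | 0.5 | 12 | 69% | 89% |
| 2 | 1 | 9 | 45% | 66% |
| 5 | 0.5 | 7.5 | 34% | 51% |
| 5 | 1 | 0 | 5% | 5% |

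The documents fix neither k nor g, so the table shows a range and is not an estimate. The expected between-arm difference at 6 months does not involve the baseline recording and stays at 15 for every k and g.

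**The case against.** The sponsor has a fair reply. Section 4.2 states the rule plainly, Section 4.2.1 and Appendix II already call the first recording baseline, and Section 6.1 refers to Section 4 for the detail of the evaluations. Section 11 mentions the home recording before delivery of the intervention, and courier delivery may itself delay the first tablet. The latency power text points to the PSQI, whose baseline precedes randomisation. All of this stands, and it limits the point to a conflict between sections with a conditional consequence.

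A reader might infer more from Appendix I, namely that its footnote 4 leaves no room for a tablet-free baseline and that recordings will therefore be made on tablets. The documents do not support that. Footnote 4 is attached to the side-effect cell, whereas the actigraphy cell carries footnote 3. The single mark under footnote 4 also stands for biweekly contacts over the rest of the study, so the column cannot be a strict day-10 limit for that row. Table E leaves room.

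A reader might also take one row of the power table as the expected loss, or carry the concern over to the primary outcome. Neither follows. The size rests on two unknowns, and baseline neurocognitive testing precedes randomisation.

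The reply does not remove the gap itself. Delivery time is not a safeguard, the headings point away from Section 4.2, and no instruction orders the recording and the first tablet.

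**Conclusion.** The point holds as an unreconciled conflict. Section 4.2 requires the five-day actigraphy and diary baseline before the intervention, Table E and Appendix I list it as an on-treatment evaluation, and no section fixes the first tablet relative to it.

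A bias arises only if four conditions hold together: tablets precede or overlap the recording, actigraphy or diary is the measure analysed, change from that recording is used, and some effect is present within days. Its direction is then toward no difference. Its size cannot be derived from the documents and, under the stated assumptions, could be anything from nothing to the whole effect. The primary neurocognitive outcome, the PSQI baseline and a comparison of 6-month values not adjusted for that recording are untouched. The correction is worth making because the baseline recording is taken once and the remedy is small.

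**What to change.** - Reconcile Section 6.2 with Table E, Section 11 and Appendix I against Section 4.2, so that the first five-day recording appears as the baseline assessment that Section 4.2 describes. It may follow randomisation.
- Show the first side-effect check as a separate entry timed from drug start, as its footnotes already define it.
- Use the MEMS data (Sections 4.5.1 and 10.1; a cap opening is only a proxy for taking a tablet) and the contact at the end of the first week on drug (Section 4.5.2) to identify any first recording made after dosing began. Do this in the same way in both arms, under blinding.
- Do not use such a recording as a baseline value. Keep the participant and compare the arms on follow-up values for that measure.

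The sponsor must settle when tablets start as part of reconciling these sections; no start day is proposed here. Section 6.3 counts about six months from the completion of baseline measures, so the revised text should also say whether the home recording starts that clock.

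The cost is schedule wording, one added question at an existing call and one date check per participant. No new visit or device is needed.

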7.0 EVALUATION CRITERIA

7.1 Response Criteria

Three domains of neurocognitive functioning will be evaluated as primary study outcomes 1) attention, 2) memory, and 3) executive functioning. These will be examined at the 6 month interval. The secondary outcomes will be evaluated by subjective and objective sleep parameters assessed at the 3 month and 6 month time periods.

Response in the neurocognitive functioning domains of attention, memory, and executive functioning will be documented as either 1) Improvement; 2) No change; or 3) Worsened. The same responses will be used for sleep onset latency. Correlative psychosocial measures of health-related quality of life and psychological distress will be examined at 6 months of melatonin/placebo treatment.

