In addition to analyzing the differences for each subscale we will also analyze the data in an alternative manner as follows. For each subscale an improvement will be defined if the difference in the Z-score (follow-up time point – baseline) is greater than 0.6 units (≥ 0.6). Let us assume that the probability of observing an improvement in a subscale in an individual in the placebo group is about 5% and then the total of 6 subscales (assuming them to be independent with the same probability of improvement) will follow a Binomial distribution $B(6, 0.05)$ with a mean of 0.3 and SD of 0.54. If we assume that the probability of improvement to be higher say about 12% in the melatonin group then the total score in that group will follow a Binomial distribution $B(6, 0.12)$ with a mean of 0.72 and SD of 0.80. Then, we will use two-sample Behrens-Fisher t-statistic to compare the two means. With a sample size of between 65 and 67 in each group we will have roughly 90% power to detect a difference of 0.42 units with type I error control $\alpha=0.05$.

Secondary Objective: Evaluate the efficacy of melatonin treatment on delayed sleep onset latency in long-term childhood cancer survivors.

- Hypothesis 2: Long-term survivors of childhood cancer with delayed sleep onset latency at baseline (Cohorts 2 and 3), randomized to the melatonin treatment arm, will demonstrate improved sleep onset latency following six months of treatment compared to the placebo groups.

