The primary interest of Objective 2 is to assess the efficacy of melatonin on delayed sleep onset latency in adult survivors of childhood cancer, which will be evaluated in Cohorts 2 and 3. We hypothesize that survivors randomized to the melatonin treatment arm will evidence a greater improvement in sleep onset latency compared to survivors randomized to placebo. The CCSS cohort mean and SD for sleep onset latency among participants with delayed sleep onset latency (i.e. $SOL \geq 30$ minutes) is 46.2 and 27.7 minutes, respectively. The test-retest correlation for sleep onset latency from the PSQI has been observed to be in the range of 0.70. Following the justification set forth in Aim 1, and assuming the SD to be 27.7, we will need to randomize 131 and 133 survivors between the melatonin and placebo arms in Cohort 2 and Cohort 3, respectively, to see an improvement of 15 minutes in sleep onset latency with 80% power with type I error control $\alpha=0.05$. The analysis for Aim 2 will be completed using a two-sample t-test.

Secondary Objective: Investigate whether improvement in sleep onset latency due to melatonin treatment is associated with neurocognitive improvement in long-term childhood cancer survivors.

- Hypothesis 3: Improvement in sleep onset latency with melatonin treatment will result in improved neurocognitive performance in long-term childhood cancer survivors who have both comorbid sleep onset latency and neurocognitive deficits at baseline (Cohort 2).

The secondary interest of Objective 2 is to investigate the association between

sleep onset latency and specific neurocognitive processes in survivors with comorbid sleep and neurocognitive dysfunction [Cohort 2]. We hypothesize that decreased sleep onset latency following 6 months of melatonin treatment will be associated with improved neurocognitive performance. With a sample size of 131 in Cohort 2 [66 randomized to melatonin, 65 randomized to placebo] we will have 80% power to detect a correlation of at least 0.25 between reduced sleep onset latency and improved neurocognitive performance with type 1 error control $\alpha=0.05$.

Exploratory Objective: Explore the association between endogenous melatonin levels and improvement in sleep onset latency.

- Exploratory Hypothesis 1: Improvement in sleep onset latency following melatonin treatment will be independent of baseline endogenous melatonin levels.

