11.2 Summary of Primary and Secondary Objectives

Primary and Secondary Summary of Objectives

Objective #	Objective Type	Analysis #	Resp Party	Stat	Safety	Analysis Measure	Analysis Title	Data Collection Time Frame	# of Participants
1.1	P	1	TB	KS	N	Patient Neurocognition	Compare neurocognitive function by treatment group	Baseline 6 month	232
2.1	S	1	TB	KS	N	Patient Sleep onset latency	Compare sleep onset latency by treatment group	Baseline 3 month 6 month	226
2.2	S	1	TB	KS	N	Patient Neurocognition and Sleep onset latency	Evaluate impact of sleep on neurocognitive function	Baseline 6 month	131
3.1	E	1	TB	KS	N	Patient Melatonin	Evaluate endogenous melatonin levels	Baseline 6 month	395
3.2	E	1	TB	KS	N	Patient Melatonin, Neurocognition Sleep onset latency	Evaluate association between endogenous melatonin and sleep	Baseline 6 month	395

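### Sleep onset latency at 3 months is assigned to the sleep objective, but the only named Hypothesis 2 test is a 6-month two-sample t-test that cannot use it

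*Combined protocol and SAP*

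**What the plan says.** Four places give the 3-month sleep data a purpose.

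- Section 6.2: at 3 months "participants will complete objective and subjective sleep measures at home, including five days of actigraphy, a daily sleep diary, and standardized sleep measures", and "These data will allow for the examination of short-term effects of melatonin on sleep parameters". Section 4.2 and the appendix schedules list the same three time points.
- Section 7.1: "The secondary outcomes will be evaluated by subjective and objective sleep parameters assessed at the 3 month and 6 month time periods".
- Section 11.2, row 2.1: the analysis title is "Compare sleep onset latency by treatment group" and the data time frame is "Baseline 3 month 6 month".

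The analysis text is narrower. In Section 11.0, Hypothesis 2 is that melatonin participants in Cohorts 2 and 3 "will demonstrate improved sleep onset latency following six months of treatment compared to the placebo groups". The sample size is set for an "improvement of 15 minutes in sleep onset latency with 80% power with type I error control" at 0.05, by the same reasoning as Aim 1, which works with a follow-up-minus-baseline difference at two time points. The method is one sentence: "The analysis for Aim 2 will be completed using a two-sample t-test". Secondary Aim 1 in the Protocol Summary says the same.

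Section 11.0 contains no repeated-measures model, no method for a 3-month comparison, no analysis set and no rule for missing values.

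**The concern.** A two-sample t-test of 6-month change has one number per participant. It has no place for a 3-month value, and a participant without a 6-month value contributes nothing. The plan therefore promises a use for the 3-month data that its only named method cannot deliver.

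Three things are at stake.

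- **Bias.** Someone who gives 3-month data and then withdraws or is lost has a known early response, and that response may be connected with leaving. The off-study list in Section 8.1 includes participant request, unacceptable toxicity and need for a disallowed medicine, so departure related to sleep or tolerability is plausible.
- **Precision.** Some information already collected goes unused.
- **Choice after the fact.** With 3-month data attached to the objective but no method written down, the choice between a 3-month, a 6-month and a combined analysis stays open until the results are visible.

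**Working it through.** **1. The plan's own sample size.** Inputs from Section 11.0: difference 15 minutes, SD 27.7, power 80%, alpha 0.05; two-sided as in Aim 1.

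n per arm = 2 × (1.960 + 0.842)² × 27.7² / 15² = 53.5, so 54 per arm and 108 in total (110 with the t distribution). The stated totals are 131 (Cohort 2) and 133 (Cohort 3). They are close to what two-sided alpha 0.025 gives: 2 × (2.241 + 0.842)² × 27.7² / 15² = 64.8, so 130 in total (134 with t). That mismatch is a separate matter and does not affect this point.

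**2. What the 3-month value adds beyond baseline.** The only latency correlation in the documents is the PSQI test-retest figure of 0.70. Assume it holds between every pair of the three visits. The 3-to-6-month correlation given baseline is then

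(0.70 − 0.70²) / (1 − 0.70²) = 0.21 / 0.51 = 0.41, so R² = 0.17.

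For a likelihood-based model, the variance of the 6-month contrast relative to baseline-adjusted completers is (1 − R²) + R² × n6/n3. Assume 25% are missing at 6 months, so n6 = 0.75N.

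| Leavers with 3-month data | n3 | Variance ratio | Reduction |
|---|---|---|---|
| Half | 0.875N | 0.83 + 0.17 × 0.857 = 0.976 | 2.4% |
| All | N | 0.83 + 0.17 × 0.75 = 0.958 | 4.2% |

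**3. What baseline adjustment adds.** In units of the single-visit variance, a change score has variance 2 × (1 − 0.70) = 0.60 and a baseline-adjusted outcome has 1 − 0.70² = 0.51. The ratio 0.51/0.60 = 0.85 is a 15% reduction. It needs no 3-month data.

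**4. The effect of the 3-month data on power** (SD 27.7, two-sided 0.05, normal approximation, R² = 0.17).

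- 131 randomized, 25% lost: about 98 remain and power is 76.5%. With 3-month data it is 77.5% (half of leavers) or 78.3% (all).
- 175 randomized so that 131 have outcomes (131/0.75 = 175): 87.3% rises to about 88.7% if all leavers have 3-month data.

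**5. Bias, under an assumed dropout pattern.** Simulation with SD 27.7, correlation 0.70 between all visits, 25% loss in each arm and 3-month data for every leaver. Leaving is random on melatonin. On placebo its odds rise 1.5- to 3-fold per SD of worse 3-month change. The completers' 6-month contrast is off by about 1.0 to 2.5 minutes, here understating any benefit. An analysis that uses the 3-month value is within 0.1 minute of the truth. Against the planned 15 minutes the error is 7% to 17% (1.0/15, 2.5/15). Against the 6.8-minute effect of the six-month trial described in Section 2.2.2, it is 15% to 37% (1.0/6.8, 2.5/6.8). The reverse pattern would reverse the sign. The documents give no dropout pattern, so this shows a possible size only.

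**The case against.** A reader might infer that the plan restricts Hypothesis 2 to 6-month data by rule, so that a quarter of participants drop out of it. The documents do not support that, for three reasons.

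- Section 7.1 and row 2.1 of Section 11.2 attach 3-month data to this objective, and no section states an exclusion rule. The intention to use the data is on paper; the method is missing.
- Under Section 6.3, participants who cannot return to campus are mailed the 6-month sleep measures, and under Section 7.3 poor adherence does not remove anyone. Those affected are participants who withdraw or are lost, not those who only miss the visit.
- The 25% loss comes from the Primary Aim paragraph, whose neurocognitive battery needs the return visit. Loss for sleep data completed at home may be lower. The number leaving after month 3 is not given.

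These points stand, and they set the limits of the finding.

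It can also be said that power is already protected. The Protocol Summary treats 131 and 133 as participants with outcome data, and at those numbers power is about 87% at two-sided 0.05. That stands for power (Section 11.0, however, gives the same numbers as those to randomize), but extra numbers do not remove bias.

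Larger efficiency claims are tempting too. Reductions of 4% to 12% follow if the raw 3-to-6-month correlation is taken as 0.5 to 0.7. In a model that adjusts for baseline, the relevant correlation is 0.41, and the gain falls to 2% to 4%.

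None of this supplies a method for the 3-month data or a missing-data rule.

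**Conclusion.** The point holds as an inconsistency and a gap in the analysis plan for a secondary efficacy objective. The 3-month latency data are promised a role, and the one named test cannot give them one or include participants without 6-month sleep data.

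The precision at issue is small: about 2% to 4% of variance from the 3-month values, or 1 to 2 points of power at 131 randomized with 25% lost. The larger gain, about 15%, comes from adjusting for baseline. Both rest on a 0.70 correlation across all visits; the first also rests on 25% missing at 6 months. The documents establish neither for this outcome.

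The stronger reason to act is bias and the open choice of analysis. Bias protection is conditional: a mixed model corrects for dropout that depends on observed latency, not on values never seen, and the documents do not say which applies. The change is worth making because it is cheap and uses data already planned.

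**What to change.** In Section 11.0 (Hypothesis 2) and Secondary Aim 1 of the Protocol Summary, replace the t-test within each cohort with:

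- **Outcome:** sleep onset latency at 3 and 6 months on one named measure. PSQI latency is a natural candidate: the sample-size paragraph takes its correlation from the PSQI, and Table D places the standardized sleep measures at the baseline visit before randomization. Section 11.0 puts the first actigraphy after randomization.
- **Model:** repeated-measures mixed model with arm, visit, arm-by-visit, baseline latency and baseline-by-visit, and unstructured covariance.
- **Analysis set:** all randomized participants with any post-baseline value.
- **Contrasts:** the 6-month arm difference is the Hypothesis 2 test; the 3-month arm difference is the short-term effect named in Section 6.2.
- **Sensitivity analysis:** one that lets missingness depend on unobserved latency, for example shifting the imputed 6-month values of leavers over a stated range.

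Then reconcile Sections 6.2, 7.1, 11.0 and 11.2 so that each names the same time points and roles.

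Cost: revised analysis wording, slightly more programming, and reliance on a missing-at-random assumption that the sensitivity analysis probes. No new visits or data are needed.
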